3.1.2 Durvalumab monotherapy

Risks with durvalumab include, but are not limited to, diarrhea/colitis and intestinal perforation, pneumonitis/ILD, endocrinopathies (hypo- and hyper-thyroidism, type I diabetes mellitus, hypophysitis and adrenal insufficiency) hepatitis/increases in transaminases, nephritis/increases in creatinine, pancreatitis/increases in amylase and lipase, rash/pruritus/dermatitis, myocarditis, myositis/polymyositis, other rare or less frequent inflammatory events including neurotoxicities, infusion-related reactions, hypersensitivity reactions and infections/serious infections.

For information on all identified and potential risks with durvalumab please always refer to the current version of the durvalumab IB.

Further information on these risks can be found in the current version of the durvalumab IB.

In monotherapy clinical studies AEs (all grades) reported very commonly ($\geq 10\%$ of patients) are fatigue, nausea, decreased appetite, dyspnea, cough, constipation, diarrhea, vomiting, back pain, pyrexia, asthenia, anemia, arthralgia, peripheral edema, headache, rash, and pruritus. Approximately 9% of patients experienced an AE that resulted in permanent discontinuation of durvalumab and

approximately 6% of patients experienced an SAE that was considered to be related to durvalumab by the study investigator.

The majority of treatment-related AEs were manageable with dose delays, symptomatic treatment, and in the case of events suspected to have an immune basis, the use of established treatment guidelines for immune-mediated (Appendix 1).

A detailed summary of durvalumab monotherapy AE data can be found in the current version of the durvalumab IB.

4 STUDY DESIGN

4.1 Description

This is a multi-center, open label phase II with safety run-in study. This study will assess the efficacy and safety of an aromatase inhibitor (anastrozole) in combination with durvalumab in patients with hormone-receptor-positive breast cancer. The objectives are to obtain data on the clinical efficacy and to assess the safety of the drug combination.

The study will test a fixed dose of durvalumab in combination with an AI. Initially, six patients will be enrolled in the safety run-in stage. If $\leq 1/6$ patients have a DLT, then the expansion stage will be open for enrollment. If $\geq 2/6$ patients have a DLT, we will amend the protocol.

Anastrozole 1 mg daily will be taken orally (PO) starting on Day 1 of each cycle for 6 months prior to definitive surgery. After the first 6 months, the patients will continue taking the AI at the discretion of the treating physician as per standard of care.

It is acceptable to switch to another AI (letrozole 2.5 mg or exemestane 25 mg daily) for intolerance such as hot flash or joint ache attributable to the AI). In the safety run-in phase, switching to another AI is allowed only after the post DLT period.

Table 4. Dosage for durvalumab and AI combination.

Durvalumab (IV)	AI (PO)
1500 mg Q4W on Day 1 of each 28-day cycles for 6 cycles	Anastrozole 1 mg (or letrozole 2.5 mg or exemestane 25 mg, if intolerance of anastrozole) for 6 months

4.1.1 Dose expansion phase

All patients will also receive a daily dose of the aromatase inhibitor anastrozole (1 mg PO). Patients will be allowed to switch to another AI for toxicity reasons as described in section 2.5.1 at any time their treating physicians deems it necessary.

4.2 Dose Limiting Toxicity

Dose-limiting toxicities (DLTs) will be evaluated during the safety run-in phase of the trial. The period for evaluating DLTs will be the first cycle of treatment (from the time of first administration of durvalumab until the clinic evaluation prior to C2D1 dosing). Subjects who do not remain on the study up to this time for reasons other than DLT will be replaced with another subject. Grading of

DLTs will follow the guidelines provided in the Common Terminology Criteria for Adverse Events (CTCAE) version 5.0.

A DLT will be defined as any Grade 3 or higher toxicity that occurs during the DLT evaluation period and meets the criteria below. Toxicity that is clearly and directly related to the primary disease or to another etiology is excluded from this definition. The following will be DLTs:

- Any Grade 4 irAE (as defined in section 15.4.4 and 15.4.5).
- Any Grade ≥ 3 colitis.
- Any Grade ≥ 3 noninfectious pneumonitis irrespective of duration.
- Any Grade 2 pneumonitis that does not resolve to \leq Grade 1 within 3 days of the initiation of maximal supportive care.
- Any Grade 3 irAE, excluding colitis or pneumonitis, that does not downgrade to Grade 2 within 3 days of onset despite optimal medical management including systemic corticosteroids or does not downgrade to Grade ≤ 1 or baseline within 14 days.
- Liver transaminase elevation $> 8 \times$ ULN or total bilirubin $> 5 \times$ ULN.
- Grade 3 or 4 febrile neutropenia
- Any treatment interruption greater than 2 weeks due to an AE.
- Any \geq Grade 3 non-irAE, except for the exclusions listed below.

The definition excludes the following conditions:

- Grade 3 fatigue lasting ≤ 7 days.
- Grade 3 endocrine disorder (thyroid, pituitary, and/or adrenal insufficiency) that is managed with or without systemic corticosteroid therapy and/or hormone replacement therapy and the subject is asymptomatic.
- Grade 3 inflammatory reaction attributed to a local antitumor response (e.g., inflammatory reaction at sites of metastatic disease, lymph nodes, etc.).
- Concurrent vitiligo or alopecia of any AE grade.
- Grade 3 infusion-related reaction (first occurrence and in the absence of steroid prophylaxis) that resolves within 6 hours with appropriate clinical management.
- Grade 3 or 4 neutropenia that is not associated with fever or systemic infection that improves by at least 1 grade within 3 days. Grade 3 or Grade 4 febrile neutropenia will be a DLT regardless of duration or reversibility.
- Grade 3 or 4 lymphopenia.
- Grade 3 thrombocytopenia that is not associated with clinically significant bleeding that requires medical intervention, and improves by at least 1 grade within 3 days.
- Isolated Grade 3 electrolyte abnormalities that are not associated with clinical signs or symptoms and are reversed with appropriate maximal medical intervention within 3 days.

Immune-related AEs are defined as AEs of an immune nature (i.e., inflammatory) in the absence of a clear alternative etiology. In the absence of a clinically significant abnormality, repeat laboratory testing will be conducted to confirm significant laboratory findings prior to designation as a DLT.

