4.6 Withdrawal of Subjects from Study Treatment and/or Study

4.6.1 Permanent discontinuation of investigational product

An individual patient will not receive any further investigational product if any of the following occur in the patient in question:

1. An individual patient will not receive any further durvalumab if their weight falls to 30kg or less
2. Withdrawal of consent or lost to follow-up
3. Adverse event that, in the opinion of the investigator or the sponsor, contraindicates further dosing
4. Patient is determined to have met one or more of the exclusion criteria for study participation at study entry and continuing investigational therapy might constitute a safety risk
5. Any AE that meets criteria for discontinuation as defined in Section 10.3 and Appendix 1.
6. Dose-limiting toxicity (as defined in section 4.2)
7. Grade ≥ 3 infusion reaction
8. Patient noncompliance that, in the opinion of the investigator or sponsor, warrants withdrawal; e.g., refusal to adhere to scheduled visits
9. Initiation of alternative anticancer therapy including another investigational agent
10. Confirmation of PD and investigator determination that the patient is no longer benefiting from treatment with durvalumab
11. Subjects who are permanently discontinued from receiving investigational product will be followed for safety per Section 15.4 and Appendix 1, including the collection of any protocol-

specified blood specimens, unless consent is withdrawn or the subject is lost to follow-up or enrolled in another clinical study. All subjects will be followed for recurrence free survival. Subjects who decline to return to the site for evaluations will be offered follow-up by phone every 3 months as an alternative.

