			
 – Monitor patients for signs and symptoms of pneumonitis or ILD (new onset or worsening shortness of breath or cough). Patients should be evaluated with imaging and pulmonary function tests, including other diagnostic procedures as described below. – Initial work-up may include clinical evaluation, monitoring of oxygenation via pulse oximetry (resting and exertion), laboratory work-up, and high- resolution CT scan.
	Grade 1 (asymptomatic, clinical or diagnostic observations only; intervention not indicated)	No dose modifications required. However, consider holding study drug/study regimen dose as clinically appropriate and during diagnostic work-up for other etiologies.	For Grade 1 (radiographic changes only): 
 – Monitor and closely follow up in 2 to 4 days for clinical symptoms, pulse oximetry (resting and exertion), and laboratory work-up and then as clinically indicated. – Consider Pulmonary and Infectious disease consult.
	Grade 2 (symptomatic; medical intervention indicated; limiting instrumental ADL)	Hold study drug/study regimen dose until Grade 2 resolution to Grade ≤ 1 . 
 • If toxicity worsens, then treat as Grade 3 or Grade 4. • If toxicity improves to Grade ≤ 1, then the decision to reinitiate study drug/study regimen will be based upon treating physician's clinical judgment and after completion of steroid taper. 	For Grade 2 (mild to moderate new symptoms): 
 – Monitor symptoms daily and consider hospitalization. – Promptly start systemic steroids (e.g., prednisone 1 to 2 mg/kg/day PO or IV equivalent). – Reimage as clinically indicated. – If no improvement within 3 to 5 days, additional workup should be considered and prompt treatment with IV methylprednisolone 2 to 4 mg/kg/day started – If still no improvement within 3 to 5 days despite IV methylprednisolone at 2 to 4 mg/kg/day, promptly start immunosuppressive therapy such as TNF inhibitors (e.g., infliximab at 5 mg/kg every 2 weeks). Caution: It is important to rule out sepsis and refer to infliximab label for

			
 general guidance before using infliximab.

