			
 Once the patient is improving, gradually taper steroids over ≥ 28 days and consider prophylactic antibiotics, antifungals, or anti-PJP treatment (refer to current NCCN guidelines for treatment of cancer-related infections [Category 2B recommendation])^a Consider pulmonary and infectious disease consult. Consider, as necessary, discussing with study physician.
Grade 3 or 4 (Grade 3: severe symptoms; limiting self-care ADL; oxygen indicated)	Permanently discontinue study drug/study regimen.	For Grade 3 or 4 (severe or new symptoms, new/worsening hypoxia, life-threatening):	
 Promptly initiate empiric IV methylprednisolone 1 to 4 mg/kg/day or equivalent. Obtain Pulmonary and Infectious disease consult; consider, as necessary, discussing with study physician. Hospitalize the patient. Supportive care (e.g., oxygen). If no improvement within 3 to 5 days, additional workup should be considered and prompt treatment with additional immunosuppressive therapy such as TNF inhibitors (e.g., infliximab at 5 mg/kg every 2 weeks' dose) started. Caution: rule out sepsis and refer to infliximab label for general guidance before using infliximab. Once the patient is improving, gradually taper steroids over ≥ 28 days and consider prophylactic antibiotics, antifungals, and, in particular, anti-PJP treatment (refer to current NCCN guidelines for treatment of cancer-related infections [Category 2B recommendation]).^a
Diarrhea/Colitis	Any Grade	General Guidance	
For Any Grade:
 
 Monitor for symptoms that may be related to diarrhea/enterocolitis (abdominal pain, cramping, or changes in bowel habits such as increased frequency over baseline or blood in stool) or related to bowel perforation (such as sepsis, peritoneal signs, and ileus). Patients should be thoroughly evaluated to rule out any alternative etiology (e.g., disease progression, other medications, or infections), including testing for clostridium

		
 – Clostridioides difficile toxin, etc. – Steroids should be considered in the absence of clear alternative etiology, even for low-grade events, in order to prevent potential progression to higher grade event. – Use analgesics carefully; they can mask symptoms of perforation and peritonitis.

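### Section 4.2 sets a Grade 3 floor for DLTs that two of its nine listed items do not fit: it would void the Grade 2 pneumonitis item and leaves open whether lower-grade AEs count under the interruption item

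*Combined protocol and SAP*

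**What the plan says.** Section 4.2 (Dose Limiting Toxicity) gives a general definition: "A DLT will be defined as any Grade 3 or higher toxicity that occurs during the DLT evaluation period and meets the criteria below". It sets aside toxicity clearly due to the disease or another cause, and then introduces nine items as events that will be DLTs. Two of the nine are:

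- "Any Grade 2 pneumonitis that does not resolve to" Grade 1 or lower within 3 days of starting maximal supportive care;
- "Any treatment interruption greater than 2 weeks due to an AE".

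A list of exclusions follows. One is "Concurrent vitiligo or alopecia of any AE grade". Nothing in 4.2 says whether the defining sentence or the list prevails.

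The term is used in two operative places. Under 4.1, at most 1 of 6 patients with a DLT opens the expansion; if 2 or more of 6 "patients have a DLT, we will amend the protocol". Under 4.6.1, one reason for permanent discontinuation of investigational product is "Dose-limiting toxicity (as defined in section 4.2"). Sections 4.7, 10.3, 11.1.1 and 11.2.1 use the term or point back to 4.2 without adding to the definition.

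**The concern.** The defining sentence joins two conditions with *and*: a grade of at least 3, and a listed criterion. A Grade 2 pneumonitis can never satisfy the first, so the sentence cancels an item printed just below it. The interruption item survives the sentence, but in a narrower form, covering only AEs of Grade 3 or higher.

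The stake is a small count with a sharp cut. If one run-in patient already has a DLT, the classification of one further event decides between 1 of 6 and 2 of 6, and so between opening the expansion and amending the protocol. For the patient concerned it also decides between a permanent stop and a possible restart. In both respects the literal sentence is the more permissive reading.

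**Working it through.** No stated figure in the plan bears on this point, so the check is mainly a comparison of texts.

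**1. Do the nine items fit the Grade 3 floor?**

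| Item in 4.2 | Fits the floor? |
|---|---|
| Grade 4 irAE | Yes |
| Colitis, Grade 3 or higher | Yes |
| Noninfectious pneumonitis, Grade 3 or higher | Yes |
| Grade 2 pneumonitis, unresolved at 3 days | No, it can never apply |
| Grade 3 irAE, not downgrading in time | Yes |
| Transaminases > 8 × ULN or bilirubin > 5 × ULN | Yes: the Appendix places Grade 3 above 5 × and 3 × ULN |
| Febrile neutropenia, Grade 3 or 4 | Yes |
| Interruption over 2 weeks due to an AE | No grade given, so open |
| Non-irAE, Grade 3 or higher | Yes |

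Seven fit and two do not.

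**2. Which reading was intended?** The list is introduced as a statement of what will be DLTs. The pneumonitis item carries its own grade and its own 3-day rule, and has no purpose unless it counts. The exclusion for vitiligo or alopecia at any grade would be partly redundant under a Grade 3 floor. For pneumonitis, then, the list governs. The interruption item is different: it still has meaning with the floor applied, so nothing in the text forces the any-grade reading.

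**3. Can a lower-grade AE cause an interruption of more than 2 weeks?** Yes, by two routes.

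- *Durvalumab.* For Grade 2 diarrhea or colitis the Appendix holds durvalumab, starts steroids, and allows a restart only after the taper: "Once the patient is improving, gradually taper steroids over" at least 28 days. No other 4.2 item covers Grade 2 colitis. Suppose the taper starts on day *t* and lasts the minimum. It ends on day *t* + 28. Cycle 2 is due on day 29, so the delay is *t* + 28 − 29 = *t* − 1 days, which exceeds 14 when *t* is 16 or later. With the ± 3 day visit window (due day 26 to 32), the threshold runs from *t* = 13 (13 + 28 − 26 = 15) to *t* = 19 (19 + 28 − 32 = 15).
- *Aromatase inhibitor.* The item does not say which treatment is interrupted. Section 7.1.1 accepts holds of up to 14 consecutive days and bars switching inside the DLT window. A hold that runs past 14 days for a Grade 2 toxicity can fall wholly within a 28-day cycle.

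**4. What follows from each reading?** If such an event is a DLT, 4.6.1 ends durvalumab. If it is not, the Appendix applies. For Grade 2 colitis durvalumab can resume after the taper. For Grade 2 pneumonitis that has improved to Grade 1 or lower, "then the decision to reinitiate study drug/study regimen will be based upon treating" physician's judgment, again after the taper. With one other DLT among the six, the count is 1 + 0 = 1 on one reading and 1 + 1 = 2 on the other.

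**5. Sensitivity of the rule, on assumed rates only.** With a per-patient DLT rate *p*, the chance that the expansion opens is (1 − *p*)^6 + 6*p*(1 − *p*)^5. At an assumed *p* = 0.10 this is 0.531 + 0.354 = 0.886. If counting lower-grade events raised the rate by an assumed 0.02 or 0.05, it would be 0.844 or 0.776. Over assumed *p* from 0.05 to 0.20 and increments from 0.01 to 0.05, the drop is about 1 to 12 percentage points. This shows how the rule responds, not how often such events occur.

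**The case against.** The best case against is that this is a drafting mismatch with little practical effect. An investigator who reads a specific Grade 2 pneumonitis item would apply it. Reaching 2 of 6 leads to an amendment, not closure. On either reading durvalumab is held for Grade 2 pneumonitis and restarted only after the taper. Section 4.6.1 also allows permanent discontinuation for an AE without a DLT. Section 7.1.1 ends study treatment for a patient who cannot resume the AI after a 14-day hold, whatever the grade. The Protocol Monitoring Committee meets monthly (16.2).

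Most of that stands, and it limits the size of the point. It does not supply the missing rule for the interruption item. The discontinuation provisions protect the individual patient, but they do not say whether that patient adds to the count of six.

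Two stronger readings are tempting. A reader might infer that the pneumonitis item has two equally live interpretations; the list's own wording is too specific for that. A reader might also infer that one unresolved Grade 2 pneumonitis would meet both items, because the taper pushes cycle 2 more than 2 weeks late. The documents do not support this. If the pneumonitis item makes the event a DLT, 4.6.1 has already ended durvalumab and no cycle 2 dose remains to be delayed. The Appendix also starts the taper when the patient is improving, not on reaching Grade 1, so no fixed delay follows.

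**Conclusion.** The concern holds in a limited form. The defining sentence in 4.2 is wrong as written: it conflicts with two of nine items, and its literal reading is the less cautious one. For Grade 2 pneumonitis the intended answer is clear and the sentence simply contradicts it. For the interruption item the answer is open for AEs of Grade 2 or lower.

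The reach is the six run-in patients. The expansion decision turns on the wording only if such an event occurs alongside exactly one other DLT (or if two such events occur with no other DLT), and the documents give no rate from which to estimate that. This is a minor but worthwhile correction to an operative safety rule. It does not show that the run-in is unsafe or that its 1-of-6 threshold is unsound.

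**What to change.** Change the wording of 4.2 only.

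1. Replace the defining sentence with: *A DLT is any toxicity, whatever its grade, that arises in the DLT evaluation period and satisfies at least one of the following criteria.*
2. Keep "Any treatment interruption greater than 2 weeks due to an AE" and add: *of any grade, where that AE began during the DLT evaluation period*. This is what the item says on its face, and it ties the item to the onset of the AE, because a durvalumab interruption begins only when the cycle 2 dose is missed.

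Keep the other-cause sentence, all the exclusions and the evaluation window as they stand.

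The cost is one amendment, with no added patients, visits or tests. A few lower-grade events will count as DLTs and end durvalumab for those patients. An interruption caused by a cycle 1 AE may be classified only after cycle 2 was due: the first day more than 14 days late is day 29 + 15 = 44, or day 32 + 15 = 47 at the end of the visit window. If that patient is the one on whom the count depends, the expansion decision waits until then.

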4.7 Replacement of subjects

Patients enrolled in the safety run-in phase of the study may be replaced if they are not evaluable for DLT (i.e., patients did not receive study treatment or withdrawn from the study for reasons other than drug-related toxicity) will need to be replaced to provide adequate evaluation of safety at the tested dose level.

Patients enrolled in the safety run-in phase who withdraw from the study after completing the first treatment cycle (DLT period) will not need to be replaced on the study.

Patients enrolled in the expansion phase of the study will not be replaced.

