11.2 Methods of statistical analyses

11.2.1 Safety Analyses

Safety data will be summarized for all patients receiving at least 1 dose of study treatment.

All patients who receive any study treatment will be included in the final summaries and listings of safety data. Detailed information collected for each AE will include a description of the event, duration, severity, relatedness to study drugs, action taken, and clinical outcome. Severity of the AEs will be graded according to the CTCAE version 5.0.

The DLT analysis will include the 6 DLT evaluable subjects enrolled in the safety run-in phase who must have had the opportunity to be on treatment for 1 cycle (4 weeks) from the initial dosing of durvalumab and received at least 1 dose of AI and one dose of durvalumab.

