- Its relationship to each of the study drugs (definite, probable, possible, unlikely, and not related).
- Its duration (start and end dates or if continuing at final exam).
- Action taken (no action taken; study drug dosage adjusted/temporarily interrupted; study drug permanently discontinued due to this adverse event; concomitant medication taken; non-drug therapy given; hospitalization/prolonged hospitalization).
- Whether it constitutes an SAE.

All adverse events will be treated appropriately. Such treatment may include changes in study drug treatment as listed in the dose interruption and modification section of this protocol (see section 7.1 for guidance). Once an adverse event is detected, it should be followed until its resolution, and assessment should be made at each visit (or more frequently, if necessary) of any changes in severity, the suspected relationship to the study drug, the interventions required to treat it, and the outcome.

Information about common side effects already known about the study drugs drug are described in the drug information section (section 3.1), the most recent investigator brochures (for durvalumab), and the FDA-approved product labels (for the three AIs). This information will be included in the patient informed consent and will be discussed with the patient during the study as needed.

All adverse events will be recorded in the subject specific AE log.

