15.3.4 Adverse events of special interest

An adverse event of special interest (AESI) is one of scientific and medical interest specific to understanding of the Investigational Product and may require close monitoring and rapid communication by the investigator to the sponsor. An AESI may be serious or non-serious. The rapid reporting of AESIs allows ongoing surveillance of these events in order to characterize and understand them in association with the use of this investigational product.

AESIs for durvalumab include but are not limited to events with a potential inflammatory or immune-mediated mechanism and which may require more frequent monitoring and/or interventions such as steroids, immunosuppressants and/or hormone replacement therapy. These AESIs are being closely monitored in clinical studies with durvalumab monotherapy and combination therapy. An immune-related adverse event (irAE) is defined as an adverse event that is associated with drug exposure and is consistent with an immune-mediated mechanism of action and where there is no clear alternate etiology. Serologic, immunologic, and histologic (biopsy) data, as appropriate, should be used to support an irAE diagnosis. Appropriate efforts should be made to rule out neoplastic, infectious, metabolic, toxin, or other etiologic causes of the irAE.

If the Investigator has any questions in regards to an adverse event (AE) being an irAE, the Investigator should promptly contact the Principal Investigator.

AESIs observed with durvalumab include:

- Diarrhea / Colitis and intestinal perforation
- Pneumonitis / ILD
- hepatitis / transaminase increases
- Endocrinopathies (i.e. events of hypophysitis/hypopituitarism, adrenal insufficiency, hyper- and hypothyroidism and type I diabetes mellitus)
- Rash / Dermatitis
- Nephritis / Blood creatinine increases
- Pancreatitis / serum lipase and amylase increases
- Myocarditis
- Myositis / Polymyositis
- Neuropathy / neuromuscular toxicity (e.g. Guillain-Barré, and myasthenia gravis)
- Other inflammatory responses that are rare / less frequent with a potential immune-mediated aetiology include, but are not limited to, pericarditis, sarcoidosis, uveitis and other events involving the eye, skin, haematological and rheumatological events.

- In addition, infusion-related reactions and hypersensitivity/anaphylactic reactions with a different underlying pharmacological etiology are also considered AESIs.

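### Read literally, the DLT list in 4.2 omits an immune-related event recorded outright as Grade 5, and 4.2 and 4.7 then disagree on replacing that patient

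*Combined protocol and SAP*

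**What the plan says.** Section 4.1 enrols six patients in the run-in. At most one DLT opens expansion; two or more lead to an amendment. Section 4.2 sets two conditions for a DLT: Grade 3 or higher, and a match with a listed criterion.

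For irAEs in general the list has two lines: "Any Grade 4 irAE (as defined in section 15.4.4 and 15.4.5"), and Grade 3 that does not downgrade in the stated time. Colitis and noninfectious pneumonitis are listed at Grade ≥ 3. The catch-all is also open-ended upwards but covers non-immune events only: "Grade 3 non-irAE, except for the exclusions listed below". Two lines do not depend on grade: the liver laboratory limits, and "Any treatment interruption greater than 2 weeks due to an AE". Section 15.3.1 grades events from 1 to 5, so Grade 5 can be recorded.

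Replacement in the run-in is described twice. Section 4.2: "Subjects who do not remain on the study up to this time for reasons other than DLT will be replaced with another subject". Section 4.7 treats as not evaluable those who were untreated or "withdrawn from the study for reasons other than drug-related toxicity". Section 11.2.1 adds that DLT-evaluable patients "must have had the opportunity to be on treatment for 1 cycle (4 weeks) from the initial dosing of durvalumab".

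**The concern.** Two general irAE lines name Grade 3 and Grade 4, and neither extends to Grade 5. The open-ended lines cover only colitis, pneumonitis and events that are not immune-related. An immune death of another kind, recorded outright as Grade 5, therefore fails the second half of the DLT definition. A non-downgrading Grade 3 irAE counts, while a fatal one may not.

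That patient also exposes a mismatch in the replacement rules, because 4.2 asks whether she left for a DLT and 4.7 asks whether she left for drug-related toxicity. At stake is the count that decides whether expansion opens: whether the death is in the numerator, and whether the patient is among the six.

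**Working it through.** **Step 1: test one event against each line of 4.2.** Take myocarditis (a listed event of special interest in 15.3.4), recorded in cycle 1 directly as Grade 5.

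| Line in 4.2 | Met? |
|---|---|
| Grade 4 irAE | No, recorded as 5 |
| Colitis, Grade ≥ 3 | No |
| Noninfectious pneumonitis, Grade ≥ 3; persistent Grade 2 pneumonitis | No |
| Grade 3 irAE not downgrading | No, recorded as 5 |
| Liver laboratory limits | Only if exceeded |
| Febrile neutropenia | No |
| Interruption over 2 weeks | Only if treatment was already held that long |
| Grade ≥ 3 non-irAE | No, it is an irAE |

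No line applies, and no other section makes a treatment-related death a DLT.

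**Step 2: cases that do count.** Section 15.3.1 says "assessment should be made at each visit (or more frequently, if necessary) of any changes in severity", so a fatal irAE first recorded as Grade 4, or as Grade 3 that did not downgrade, is already a DLT. A death with no immune diagnosis falls under the non-irAE line unless clearly due to the disease or another cause. The gap is what remains.

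**Step 3: replacement of the patient in the gap.** Under 4.2 she left for something other than a DLT, so she is replaced. Under 4.7 the test is drug-related toxicity. By 15.3.4 an irAE "is defined as an adverse event that is associated with drug exposure", so by implication she is not replaced. Section 11.2.1 leans towards keeping her, since she had the opportunity for a full cycle, but it does not settle the matter. She could also miss the run-in safety set in 11.1.1, which needs adverse events recorded at all visits to C2D1, or a DLT.

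**Step 4: size.** The plan states no operating characteristics for the run-in, so there is no figure to reproduce. The nearest rate in the documents is about 6% durvalumab-related SAEs of any kind on monotherapy, not limited to cycle 1 (3.1.2). Assumptions:

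- f, cycle 1 Grade 5 irAE rate per patient: 0.5 to 1% (0.5/6 = 8% to 1/6 = 17% of that SAE figure)
- g, share of those falling in the gap: 20 to 50%
- h = f × g = 0.001 to 0.005; with g = 1 as an upper bound, h = 0.005 to 0.01
- q, rate of listed DLTs, mutually exclusive with gap events: 10 to 30%

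The chance of at least one gap event in six is 1 − (1 − h)^6: 0.006 at h = 0.001 and 0.030 at h = 0.005.

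The chance of opening expansion is P(X ≤ 1) for a binomial with n = 6 and event rate:

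- q + h if the death is counted
- q/(1 − h) if it is not counted and the patient is replaced
- q if it is not counted and she is kept

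At q = 0.20:

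| h | Counted | Not counted, replaced | Not counted, kept | Rise, points (replaced / kept) |
|---|---|---|---|---|
| 0.001 | 0.6529 | 0.6549 | 0.6554 | 0.20 / 0.25 |
| 0.0025 | 0.6492 | 0.6541 | 0.6554 | 0.49 / 0.61 |
| 0.005 | 0.6431 | 0.6529 | 0.6554 | 0.98 / 1.23 |
| 0.01 | 0.6308 | 0.6504 | 0.6554 | 1.96 / 2.46 |

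Over q = 0.10 to 0.30 the rise is 0.15 to 1.23 points for h = 0.001 to 0.005, and 0.75 to 2.46 points for the upper bound.

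**Step 5: given that one such death has occurred** and the rule is applied literally, the chance of opening expansion is (1 − q)^5 if the death is counted, P(X ≤ 1 | 6, q) if not counted and replaced, and P(X ≤ 1 | 5, q) if not counted and kept.

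| q | Counted | Replaced | Kept |
|---|---|---|---|
| 0.10 | 0.590 | 0.886 | 0.919 |
| 0.20 | 0.328 | 0.655 | 0.737 |
| 0.30 | 0.168 | 0.420 | 0.528 |

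**The case against.** The intent is hardly in doubt. The lead sentence of 4.2 speaks of Grade 3 or higher, three neighbouring lines are open-ended upwards, and no one designing a run-in would count a stubborn Grade 3 irAE and leave out a death. An investigator would very likely count it.

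Several conditions must also hold together: an immune death in cycle 1, not colitis or pneumonitis, not past the liver limits, never recorded at Grade 4 or as non-downgrading Grade 3, and not preceded by a long hold. SAEs are reported within 24 hours (15.4) and reviewed singly in real time (16.3.3). The Protocol Monitoring Committee meets monthly and reviews all adverse events (16.2). Section 11.2.1 keeps every treated patient in the safety summaries, so the death would not vanish from the report. The 4.7 side of the conflict is by implication, in a garbled sentence that does not mention death. The rates in the calculation are assumptions multiplied together.

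Most of this stands, and it limits the weight of the point. It does not remove it: none of these safeguards makes the death a DLT or says whether the patient stays in the six. The conditional probabilities describe a rare event under a literal reading and should not be taken as the expected effect.

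**Conclusion.** The point holds as a fault in the written rule, almost certainly unintended. Followed literally, 4.2 leaves out an irAE recorded outright as Grade 5, apart from the carve-outs above. One such death plus one other DLT then reads 1/6 and opens expansion, where 2/6 should trigger an amendment. The expected effect is small: 0.15 to 1.2 percentage points on the chance of opening expansion, and up to about 2.5 points if every assumed Grade 5 irAE fell in the gap. These sizes rest on assumed rates; the textual finding does not. The primary endpoint and the Simon design are unaffected. It should be corrected in the next amendment because the consequence, if it arose, is serious and the correction is nearly free.

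**What to change.** Change the first irAE bullet in 4.2 to *Any Grade ≥ 4 irAE*. The fatal case is then a DLT, 4.2 and 4.7 agree that the patient is not replaced, and she enters the 11.1.1 run-in set through its DLT clause. While editing that bullet, correct its cross-reference: the irAE text is numbered 15.3.4 and 15.3.5, not 15.4.4 and 15.4.5.

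Separately, state one replacement rule in both 4.2 and 4.7: a patient with a DLT, including a drug-related death, is never replaced. The two sections also differ on withdrawal in cycle 1 for drug toxicity below DLT level, and the Grade ≥ 4 change does not resolve that. Such a patient is not fully observed, so the sponsor should choose a handling and state it once.

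The cost is one symbol, one shared sentence and one sponsor decision, made in the next IRB-approved amendment. No patients, procedures or analyses are added.
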